2.3.1. Risk Assessment

Potential Risk of Clinical Significance	Summary of Data / Rationale for Risk	Mitigation Strategy
Investigational Medicinal Product (IMP) GSK3494245		
Kidney	
 Kidney tubular dilatation, tubular basophilia and interstitial inflammatory cell infiltration was noted in male and female mini-pigs dosed at 300 mg/kg/day Based on in vitro data, GSK3494245 has the potential to inhibit renal transporters involved in the excretion of creatinine. 	
Inclusion criteria:
 
 Urinary analysis at screening to be free of blood and protein. If trace protein or blood is found, a repeat test will be performed within 24 hrs, or as soon as possible within screening period. 
Exclusion criteria:
 
 History of current or past significant renal diseases to be excluded, e.g. Acute Kidney Injury, parenchymal kidney disease. Not to exclude history of renal calculi Screening eGFR (CKD-EPI) <90 ml/min/1.73m² Screening urine albumin:creatinine ratio >30 mg/g (>3 mg/mmol) 
Monitoring:
 
 Serum renal function and urinary analysis monitoring (first void if possible) Urine albumin: creatinine ratio (first void if possible) Urine glucose by dipstick, if dipstick is positive then send for laboratory urine

Potential Risk of Clinical Significance	Summary of Data / Rationale for Risk	Mitigation Strategy
		
glucose with contemporaneous serum glucose.
 
 • By observing the PK safety margin for renal findings by targeting up to the total daily AUC and Cmax to be below the female mini pig NOAEL (AUC_{24h} of 48700 ng×h/mL and a mean plasma Cmax of 6100 ng/mL). • Monitor for clinical symptoms of polyuria and polydipsia; if symptoms suggestive then exclude endocrine causes and quantify urine output. 
Participant withdrawal
 
 • New onset of any clinically significant and persistent (within 48 hrs) haematuria as confirmed by microscopy. • New onset of clinically significant and persistent (within 48 hrs) proteinuria (Spot Urine Albumin Creatinine (ACR) ratio ≥30mg/mmol) in the absence of another clinical explanation e.g. calculus / infection. • Change in serum creatinine >26 µmol/L (0.3 mg/dl) from baseline or > 50 % from baseline. If change in serum creatinine measures at >26 µmol/L (0.3 mg/dl), repeat within 24 hrs. If confirmed, the participant will be withdrawn. If a participant meets the

CONFIDENTIAL

208441
Protocol Amd 6

Potential Risk of Clinical Significance	Summary of Data / Rationale for Risk	Mitigation Strategy
		
withdrawal criteria for serum creatinine, then further investigations will be performed.
 
Study Stopping criteria The study will be halted if 1 or more participants across all study parts develop any of the above withdrawal criteria and it is considered to be related to GSK3494245 (in the opinion of the investigator in consultation with the Medical Monitor).
 
CCI
  
Renal transporter effects (for MAD part):
 
 For any participant with a persistent (2 consecutive readings) rise in SrCr\geq30% or a fall in eGFR\geq30% from baseline, a sample will be taking for Cystatin-C evaluation of eGFR to aid understanding of

Potential Risk of Clinical Significance	Summary of Data / Rationale for Risk	Mitigation Strategy
		
whether changes in creatinine levels are related to effects on renal transporters.
 
 • If no other renal markers are abnormal (serum urea, phosphate, potassium, calcium magnesium white blood counts, urine glycosuria, uACR), dosing of the individual participant may continue while eGFR with Cystatin-C is being evaluated. • If any other renal markers are abnormal (serum urea, phosphate, potassium, calcium, magnesium, white blood counts, urine glycosuria, uACR) in addition to a persistent rise in SrCr\geq30% or a fall in eGFR\geq30% from baseline, the participant will be withdrawn from the study (Cystatin-C still checked) • If two or more participants have a fall in eGFR\geq30% or rise in SrCr\geq30% accompanied by abnormality in any other renal markers, the study will be temporarily halted for evaluation.

CONFIDENTIAL

208441
Protocol Amd 6

Potential Risk of Clinical Significance	Summary of Data / Rationale for Risk	Mitigation Strategy
Stomach	
 Erosion of glandular region of stomach of female rats dosed at 100mg/kg/day and also in male and female rats dosed at 300 mg/kg/day 	
Contact time with stomach in humans are likely to be short (less than 2 hrs) and concentrations considered in the human study are much lower than in the Rat study.
 
Inclusion/exclusion criteria:
 
 Participants with current or history of clinically significant gastritis or gastroduodenal ulcers or regular NSAID use, will be excluded from the study based on medical history at screening. 
Monitoring:
 
 Participants will be monitored for GI symptoms reported as adverse events. 
Participant withdrawal:
 
 Any reported symptoms which in the investigator's opinion raises a clinical suspicion of gastric erosion/ulcers, will be referred to a gastro enterology specialist for further management, and endoscopy (if required).
Cardiovascular	
 Isolated Non-Sustained Ventricular Tachycardia (NSVT) - 5 episodes of >3 abnormal beats 	
Inclusion/exclusion criteria:
 
 Holter monitoring at study screening.

CONFIDENTIAL

208441
Protocol Amd 6

Potential Risk of Clinical Significance	Summary of Data / Rationale for Risk	Mitigation Strategy
	observed in one mini-pig administered low dose of 60 mg/kg only	
 Exclusion of participants with waveform abnormalities including premature ventricular contraction (PVC) triplets and more than 500 single PVCs in 24 hrs, or any other abnormalities at the discretion of investigator. 
Monitoring:
 
 In SAD: Telemetry monitoring for 24 hrs post-treatment. In MAD: Telemetry on Day 1, 0-48 hours post-treatment and Day 6 for 0-24 hours, post morning treatment). If waveform abnormality detected then extend for further 24hr. Participant withdrawal: NSVT > 3 beats or PVC triplets on telemetry.
Liver	
 Hepatocellular hypertrophy noted in female rats dosed 100mg/kg/day and male and female rats dosed at 300mg/kg/day Increase in glutamate dehydrogenase and alanine aminotransferase activities in female rats dosed at 100 mg/kg and 300 mg/kg 	
Exclusion criteria:
 
 History of current or past significant hepatic diseases excluded: HBsAg positive, HCV Ab positive (with RNA positive) Known hepatic or biliary abnormalities to be excluded.

Potential Risk of Clinical Significance	Summary of Data / Rationale for Risk	Mitigation Strategy
	
 • Increase in serum bile acids, total bilirubin, alkaline phosphatase in female rats dosed at 300 mg/kg • Hepatic inflammatory cell infiltration, portal and bile duct epithelial hypertrophy noted in male and female mini-pigs dosed at 300 mg/kg/day • Increase in sorbitol dehydrogenase and aspartate aminotransferase activities in female minipigs dosed at 300 mg/kg • Increase in serum bile acids, total bilirubin in female and male mini-pigs dosed at 300 mg/kg 	
 • Abnormal liver function tests excluded: ALT > ULN at screening or Day -1, Total Bilirubin > 1.5xULN • Consumption of >14 units/week (men) alcohol • Co-medications are excluded except for e.g. acetaminophen (capped to ≤2 grams/day) 
Monitoring:
 
 • Liver enzyme and bilirubin assessments • By observing the PK safety margin for renal findings by targeting up to exposure from female mini pig NOAEL (AUC_{24h} of 48700 ng×h/mL and a mean plasma C_{max} of 6100 ng/mL). • CCI [REDACTED] [REDACTED] [REDACTED] 
Participant Withdrawal and Study Stopping criteria as per GSK guidance on Liver Chemistry stopping criteria in Section 7.1.4.
 
 • ALT ≥ 3xULN – discontinue treatment and refer to Liver Safety Required Actions and

Potential Risk of Clinical Significance	Summary of Data / Rationale for Risk	Mitigation Strategy
		Follow up Assessments section in Appendix 5 (Section 10.5)
Olfactory	
 Olfactory epithelial degeneration observed in nasal turbinates of female rats dosed at 300mg/kg/day 	
Exclusion criteria:
 
 Current or history of change in taste or smell without any plausible clinical explanation based on the investigator's clinical judgement. 
Monitoring:
 
 As part of the medical interview and during routine physical examination, participants will be assessed for changes in smell or taste 
Participant withdrawal:
 
 New onset changes in smell which cannot be explained by other causes - following further investigations carried out as per investigator's discretion in consultation with the Medical Monitor.
Mitochondrial toxicity	
 DILIsym* modelling suggested main mechanism of DILI at doses higher than proposed therapeutic dose is mitochondrial dysfunction - compound modelled as an ATP synthesis inhibitor with ROS production. 	At the proposed maximum clinical free C _{max} , the inhibition of isolated ATP synthase was estimated to not exceed 10% at the lower 95% confidence interval, with the reduction in isolated mitochondrial respiration estimated to be lower still. It is considered that small

Potential Risk of Clinical Significance	Summary of Data / Rationale for Risk	Mitigation Strategy
		
reductions in ATP synthase and mitochondrial respiration, of the magnitude estimated for GSK3494245 at the maximum free C_{max} concentrations currently proposed for healthy human volunteer studies, would not impact overall bioenergetic reserve sufficiently to be of biological significance.
 
Monitoring:
 
 • Liver, cardiovascular, gastrointestinal, renal monitoring as outlined in mitigation strategies relating to those systems in this Section 2.3.1. • Cranial and peripheral nerve examinations • Abnormal changes in body temperature • Serial venous lactate measurements (with further investigations at the investigator's discretion to exclude other causes of hyperlactataemia and evaluate for lactic acidosis) • Serum glucose • Fasting lipids (cholesterol and triglycerides)

Potential Risk of Clinical Significance	Summary of Data / Rationale for Risk	Mitigation Strategy
		
If a participant develops acidosis (where low pH is confirmed by the Investigator) during the study, the following actions should be considered:
 
 • Measurement of serum and urine ketones, chloride and calcium to be performed contemporaneously with low pH. 
If an acidosis adverse event is observed on a venous blood gas, an arterial blood gas test may be performed if deemed appropriate by the Investigator to inform the clinical care of the participant.
 
Participant withdrawal:
 
 • Unexplained lactic acidosis • Clinical symptoms and signs and clinical chemistry and haematology parameters would be reviewed by the Investigator, Safety and Medical Governance (SMG) lead and Medical Monitor during dose escalation meetings and a decision to withdraw individual participants or stop the study

CONFIDENTIAL

208441
Protocol Amd 6

Potential Risk of Clinical Significance	Summary of Data / Rationale for Risk	Mitigation Strategy
		based on potential mitochondrial toxicity would be made following this review.
Study Procedures		
CCI		
Unblinding to potential urine colour change	During toxicokinetic studies of GSK3494245 in the Gottingen Minipig a visually detectable colour change in urine was observed post dosing, which was raised as a potential unblinding risk.	
• Urine samples will be collected in coloured or opaque collection vessels.• Independent laboratory staff will process urine samples to ensure blinding of site staff.• Coloured filters installed in lighting fixtures in the Clinical Unit in areas where participants reside.

CONFIDENTIAL

208441
Protocol Amd 6

Potential Risk of Clinical Significance	Summary of Data / Rationale for Risk	Mitigation Strategy
		
• Blue colouring of water in toilet facilities of the Clinical Unit.• Exclusion of female participants.
Other		
COVID-19	
Participation within a hospital environment may increase risk of contracting COVID-19.
 
Exposure to other participants and staff may increase risk of exposure.
	
• Monitoring of clinical presentation of COVID-19 signs/symptoms.• Conduct study at a site which has appropriate mitigation strategies in place.

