Other Tests	
 • Alcohol breath test and urine drug screen (to include at a minimum: amphetamines, methamphetamine, barbiturates, cocaine, opiates, cannabinoids and benzodiazepines, methadone, phencyclidine and tricyclic antidepressants) • Serology (HIV 1 & 2 antibody, hepatitis B surface antigen [HBsAg], and hepatitis C virus antibody). • Estimated glomerular filtration rate (eGFR) will be calculated using the creatinine-based CKD-EPI formula. Additionally, eGFR may be estimated using the Cystatin C CKD-EPI formula if for any participant there is a persistent (2 consecutive readings) rise in $SrCr \geq 30\%$ or a fall in $eGFR \geq 30\%$ from baseline, or at the PIs discretion • COVID-19 testing The results of each test must be entered into the CRF ⁵ .			

Laboratory Assessments ¹	Parameters
-------------------------------------	------------

NOTES :

1. The investigative site may assess other laboratory parameters as needed, according to standard site practice and results will be recorded in source documents.
2. Details of liver chemistry stopping criteria and required actions and follow-up assessments after liver stopping or monitoring event are given in Section 8.1.5 and Appendix 5. All events of ALT $\geq 3 \times$ upper limit of normal (ULN) and bilirubin $\geq 2 \times$ ULN (>35% direct bilirubin) or ALT $\geq 3 \times$ ULN and international normalized ratio (INR) >1.5 , if INR measured, which may indicate severe liver injury (possible Hy's Law), must be reported as an SAE (excluding studies of hepatic impairment or cirrhosis).
3. CPK cut off value will be determined at the discretion of the investigator taking into account context of change.
4. Urine phosphate to be assessed only in the event a participant has persistent hypophosphataemia. (less than 0.8mmol/L) confirmed by repeat testing.
5. The investigative site may screen for additional drugs of abuse as part of standard site practice and will be recorded in source documents. The study CRF will only collect drug screen results of those that are positive.
6. Serum chloride, calcium, ketones, sodium and bicarbonate to be measured by the local lab in the event of confirmed low pH

10.3. Appendix 3: AEs and SAEs: Definitions and Procedures for Recording, Evaluating, Follow-up, and Reporting

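### No pre-dose cystatin C is planned for the MAD part, so the transporter-versus-true-GFR reading rests on a post-trigger value set against a creatinine-based baseline

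*Protocol*

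**What the plan says.** Protocol 2.3.1 (kidney row) lists two renal concerns: tubular findings in mini-pigs, and in vitro evidence that "GSK3494245 has the potential to inhibit renal transporters involved in the excretion of creatinine". The second could raise creatinine with no loss of filtration.

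For the MAD part, 2.3.1 sets a trigger relative to the participant's own baseline. It begins "For any participant with a persistent (2 consecutive readings) rise in SrCr" and requires a creatinine rise or an eGFR fall of at least 30%. Once it is met, "a sample will be taking for Cystatin-C evaluation of eGFR to aid understanding of" "whether changes in creatinine levels are related to effects on renal transporters". If a named panel of other renal markers is normal, "dosing of the individual participant may continue while eGFR with Cystatin-C is being evaluated". If any of them is abnormal the participant is withdrawn, and cystatin C is still checked.

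Table 12 (Protocol 10.2) bases routine eGFR on creatinine. It adds that "eGFR may be estimated using the Cystatin C CKD-EPI formula if for any participant there is a persistent" change of that size, "or at the PIs discretion". Cystatin C is absent from the readable chemistry panel in Table 12 and from the readable MAD schedule (1.3.2). The readable part of SAP 5.2 plans no cystatin C analysis. Neither document says what the result is compared with, or which result points to a transporter effect.

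**The concern.** The two explanations differ in how the markers move. With pure transporter inhibition, creatinine eGFR falls and cystatin C eGFR stays where it was. With a true loss of filtration, both fall. Separating them calls for the change in each marker, and the plan supplies that change for creatinine only.

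A post-trigger cystatin C eGFR can be set against the participant's creatinine-based baseline or against the entry floor of 90 mL/min/1.73m². That floor is also creatinine-based, so no participant has been shown to start with a cystatin C eGFR of 90 or more. Either comparison includes the ordinary difference between the two markers within a person, which a paired baseline would remove. For example, a post-trigger cystatin C eGFR of 80 is no change for someone who started at 80, and a 27% fall for someone who started at 110 (1 − 80/110 = 0.27).

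The reading can matter while dosing is under way. Under 7.1.3 a confirmed creatinine rise above 26 µmol/L leads to withdrawal. A 30% rise is smaller than that whenever baseline creatinine is below 26/0.30 = 86.7 µmol/L. For those participants the cystatin C sample can come before any withdrawal criterion is met. With six active participants per cohort, errors in individual readings will not average out.

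**Working it through.** The plan states no error rate or precision for cystatin C, so there is no figure to reproduce. The check has three steps.

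**1. What a single value can show.** A true 30% fall takes an eGFR of 90 to 63, 100 to 70, 110 to 77 and 120 to 84. Only a starting value above 90/0.7 = 128.6 would still be at or above 90 afterwards. A post-trigger value therefore carries information even without a baseline, provided the two markers roughly agree in that person.

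**2. How well it separates the two explanations.** Take two normal distributions on the log scale, one for no change in true GFR and one for a true fall, with the cut at the midpoint. The misclassification probability is Φ(−d / (2·SD)), where d is the log-scale separation. Every SD below is an assumption.

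*Set A: a true 30% fall, d = ln(1/0.7) = 0.357.* Without a pre-dose value, SD is that of cystatin C eGFR against the creatinine-based baseline. With one, it is the SD of the within-person change.

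| Comparison | Assumed SD | Misclassified |
|---|---|---|
| No pre-dose value | 0.15 | 11.7% |
| | 0.20 | 18.6% |
| | 0.25 | 23.8% |
| | 0.30 | 27.6% |
| Paired pre-dose value | 0.05 | 0.02% |
| | 0.07 | 0.5% |
| | 0.10 | 3.7% |

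*Set B: a smaller signal and less favourable paired SDs.* If eGFR varies with creatinine to the power −1.2 (assumed), a 30% creatinine rise is a fall of 1 − 1.3^−1.2 = 27%, so d = 1.2 × ln 1.3 = 0.315. Without a baseline, assume a between-marker SD of 0.10 to 0.20. With one, assume a within-person CV of 5% to 10%, which gives an SD of change of CV × √2.

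| Comparison | Assumed SD | d / SD | Misclassified |
|---|---|---|---|
| No pre-dose value | 0.10 | 3.1 | 5.8% |
| | 0.15 | 2.1 | 14.7% |
| | 0.20 | 1.6 | 21.6% |
| Paired pre-dose value | 0.05√2 = 0.071 | 4.5 | 1.3% |
| | 0.07√2 = 0.099 | 3.2 | 5.6% |
| | 0.10√2 = 0.141 | 2.2 | 13.3% |

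**3. Reading the two sets together.** Misclassification is about 6% to 28% without a paired baseline and from under 1% to 13% with one. The ranges overlap, but within each set the paired comparison is better at the matching low and high assumptions. A coin toss would give 50%, so the unpaired reading is weaker but not empty.

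**The case against.** A reader might infer that cystatin C cannot answer the transporter question at all, or that no renal safety conclusion can be drawn for the MAD part. The documents do not support either.

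- The protocol claims only that the test will aid understanding, and reads it with urea, electrolytes, white counts, glycosuria and urine albumin:creatinine ratio. No withdrawal or halting rule in 2.3.1 or 7.1.3 turns on the cystatin C result. Each MAD cohort also has placebo participants. This stands, and it limits the point to how a supportive test is interpreted, in however many participants trigger it, possibly none.
- Other references may be obtainable. Section 8.4.1 lets PK plasma be used for safety questions, and each MAD participant has a Day 1 pre-dose PK sample. Table 12 allows discretionary testing with no set timing. Chemistry is drawn again 7 to 14 days after the last dose, when a drug with a half-life of about 4 hours should have cleared. These routes exist, but none is planned for this purpose. The PK sample is about 1 mL of plasma that may also go to metabolite work, and its suitability for the assay is not stated. An off-drug value would come after the dosing decision, and would mislead if an injury had persisted.
- A flat statement that no pre-dose cystatin C exists goes too far. Parts of the kidney row, the MAD schedule and Appendix 2 are redacted. The conditional wording in 2.3.1 and Table 12 argues against a scheduled sample but does not exclude one.
- Every SD, CV and exponent above is assumed. The figures show direction and rough size only.

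**Conclusion.** The point holds in a limited form. In the readable protocol, cystatin C for the MAD part is by default first measured after a sustained creatinine rise or eGFR fall of at least 30%, and no pre-dose value is planned. The within-participant change, which is the quantity that best separates a transporter effect from a true fall in GFR, cannot then be calculated. The loss is one of discrimination: roughly 6% to 28% misclassified without a paired baseline, against under 1% to 13% with one, under a two-group normal model and assumed SDs. Existing renal safeguards are not undermined. This is a cheap improvement, worth making before dosing because a true pre-dose reference is hard to recover afterwards.

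**What to change.** In Protocol 2.3.1, Table 12 and the MAD schedule (1.3.2), provide for a retained serum aliquot from the existing Day -1 or Day 1 pre-dose chemistry draw for each MAD participant. Alternatively, confirm that the pre-dose PK plasma covered by 8.4.1 is suitable in matrix and volume, and reserve it for this use. If the trigger is met, assay the stored and event samples in the same run. Report percentage change in cystatin C eGFR beside percentage change in creatinine eGFR, and state in advance that this paired comparison is how the result will be read. If a redacted part of the protocol already schedules a pre-dose sample, a cross-reference from 2.3.1 and Table 12 would be enough.

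The withdrawal and halting rules are unchanged. The cost is one aliquot for up to 40 participants from blood already drawn, freezer storage, a consent line, and short protocol and laboratory-manual wording. Assays are run only for participants who meet the trigger.

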7.1.2. Dose Escalation / Study Stopping Criteria

The Principal Investigator and the GSK Medical Monitor will review the following and study dosing **will be** stopped if any of these criteria are met:

- Two or more participants from the previous dose level on active treatment experience an AE which is of severe intensity and reasonably attributable (in the opinion of the investigator) to dosing with GSK3494245.
- One or more participants across all study parts develop an adverse renal event as defined in the renal withdrawal criteria below (Section 7.1.3) considered to be related to GSK3494245 (in the opinion of the investigator in consultation with the Medical Monitor).
- One or more participants from any dose level experiences a serious adverse event which has a reasonable possibility of relation to investigational product.
- The dose escalation/study progression will be temporarily halted, and no further dosing will occur until a full safety review of the study has taken place. Relevant reporting and discussion with the GSK medical monitor, relevant GSK personnel, regulatory authorities and the Independent Ethics Committee will then take place prior to any resumption of dosing.

All other stopping criteria will apply even if no PK stopping criteria have been met.

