7.1.3. Renal Stopping Criteria

For SAD and MAD - A participant that meets any of the following bulleted criteria will be withdrawn from the study:

- New onset of any clinically significant and persistent (within 48 hrs) haematuria as confirmed by microscopy.
- New onset of clinically significant and persistent (within 48 hrs) proteinuria (Spot Urine Albumin Creatinine (ACR) ratio $\geq 30\text{mg}/\text{mmol}$) in the absence of another clinical explanation e.g. calculus / infection.

- If there is any change in serum creatinine $> 26 \mu\text{mol/L}$ (0.3 mg/dl) from baseline or $> 50 \%$ from baseline. If change in serum creatinine measures at $> 26 \mu\text{mol/L}$ (0.3 mg/dl), repeat within 24 hrs. If confirmed, the participant will be withdrawn, and further investigations will be performed.

For MAD only - If two or more participants have a fall in $\text{eGFR} \geq 30\%$ or rise in $\text{SrCr} \geq 30\%$ accompanied by abnormality in any other renal markers, the study will be temporarily halted for evaluation.

[figure not shown]

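### In the MAD part, a confirmed creatinine rise with other renal markers normal can require withdrawal under Section 7.1.3 and permit continued dosing under Section 2.3.1, with no visible statement of which prevails

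*Protocol*

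**What the plan says.** The general rule is in Protocol Section 7.1.3: "For SAD and MAD - A participant that meets any of the following bulleted criteria will be withdrawn from the study". One listed criterion is a creatinine rise above 26 µmol/L or above 50% of baseline. A rise above 26 µmol/L is repeated within 24 hours, and then "If confirmed, the participant will be withdrawn, and further investigations will be performed". The kidney entry of the risk table in Section 2.3.1 lists the same limits as withdrawal criteria: "Change in serum creatinine >26 µmol/L (0.3 mg/dl) from baseline or > 50 % from baseline".

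Further down that entry, under renal transporter effects for the MAD part, is a second rule. "For any participant with a persistent (2 consecutive readings) rise in SrCr" of 30% or more, or with an eGFR fall of 30% or more, a Cystatin-C sample is taken. If no other renal marker is abnormal, "dosing of the individual participant may continue while eGFR with Cystatin-C is being evaluated". If another marker is abnormal, the participant is withdrawn.

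Two study-level triggers sit beside these. Section 7.1.2 (and Section 2.3.1) stops dosing if "One or more participants across all study parts develop an adverse renal event as defined in the renal withdrawal criteria below (Section 7.1.3") and the event is considered related to GSK3494245. Sections 2.3.1 and 7.1.3 add a temporary halt, introduced in 7.1.3 by "For MAD only - If two or more participants have a fall in" eGFR, or a creatinine rise, of at least 30% accompanied by another abnormal renal marker.

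Section 7.1.8 makes the renal criteria individual stopping criteria. Section 7.1 treats discontinuation as permanent, and Section 7.1.10 bars restart once any stopping criterion is met.

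**The concern.** The two participant-level rules react to the same measurement. One is defined by an absolute rise or a 50% rise and requires withdrawal. The other is defined by a 30% rise with no ceiling and, when other markers are normal, permits dosing to continue. If one creatinine result can satisfy both, two investigators following the protocol could act differently on it.

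The event is foreseeable. Section 2.3.1 lists kidney findings in mini-pigs and states that "GSK3494245 has the potential to inhibit renal transporters involved in the excretion of creatinine". The Cystatin-C step exists because the sponsor expects it may have to separate a transporter effect from a fall in filtration. A participant withdrawn under one reading cannot come back. A participant continued under the other receives further BID or TID doses while the Cystatin-C result is pending.

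There is also a gap in carry-over. The individual withdrawal rule for a change of 30% or more with another abnormal marker is in Section 2.3.1 but not in Section 7.1.3, to which Section 7.1.8 sends the reader.

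**Working it through.** The plan states no figure for this overlap, so there is nothing to reproduce. The check is whether, and where, the two trigger regions intersect.

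**Inputs.** General rule (Sections 2.3.1 and 7.1.3): rise above 26 µmol/L, or above 50% of baseline. MAD transporter rule (Section 2.3.1): rise of at least 30% on two consecutive readings. Baseline creatinine B: the documents give no distribution, so 50 to 110 µmol/L is an assumed range.

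**Formulas.** The general rule triggers at a rise above min(26, 0.5B). The transporter rule triggers at 0.3B. Both apply from max(0.3B, min(26, 0.5B)), which as a fraction of baseline is max(30%, min(26/B, 50%)). The 50% limb governs below B = 26/0.50 = 52. The two thresholds meet at B = 26/0.30 = 86.7.

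| Assumed B (µmol/L) | 30% rise | General trigger, above | Both apply | Transporter rule only |
|---|---|---|---|---|
| 50 | 15 | 25 | above 25 (50%) | 15 to 25 |
| 60 | 18 | 26 | above 26 (43.3%) | 18 to 26 |
| 70 | 21 | 26 | above 26 (37.1%) | 21 to 26 |
| 80 | 24 | 26 | above 26 (32.5%) | 24 to 26 |
| 86.7 | 26 | 26 | above 26 (30%) | none |
| 90 | 27 | 26 | from 27 (30%) | none |
| 100 | 30 | 26 | from 30 (30%) | none |
| 110 | 33 | 26 | from 33 (30%) | none |

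Below 86.7 µmol/L, every rise that meets the general rule is also at least 30%. Above 86.7, every rise of at least 30% also exceeds 26 µmol/L. There, only rises between 26 µmol/L and 30% (26 to 27 at 90, 26 to 30 at 100, 26 to 33 at 110) fall under the general rule alone. The overlap has no upper bound.

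**Can one pair of readings meet both definitions?** Yes. A repeat within 24 hours that confirms the rise also supplies two consecutive readings. The MAD schedule (Section 1.3.2) lists chemistry on nearly every dosing day.

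**Worked case.** Take a MAD participant with B = 80, two consecutive readings 28 µmol/L above baseline (28/80 = 35%), the second a repeat within 24 hours, and other renal markers normal. Section 7.1.3 withdraws. Section 2.3.1 lets dosing continue while Cystatin-C is evaluated. If another marker were abnormal, both rules would withdraw and there would be no conflict.

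**Study level.** If that rise is considered related to GSK3494245, Section 7.1.2 stops study dosing on this one participant, while the transporter text would let the same participant continue. The two-participant MAD halt is not met and has no bearing on the case.

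The eGFR limb of the transporter rule was not converted to creatinine, because the documents do not give the formula or the ages needed.

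**The case against.** The strongest reply is that the two texts differ in force. Section 7.1.3 is mandatory, names the MAD part and sits in the operative discontinuation section. The Section 2.3.1 text is permissive and interim. A permission need not cancel a separate obligation, and the same kidney entry lists the 26 µmol/L and 50% limits first. On this reading both texts are obeyed by withdrawing anyone who meets 7.1.3, and the permission covers only smaller rises, such as 18 to 26 µmol/L at a baseline of 60, and eGFR falls.

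That reading is reasonable, but it is not written down in the visible text. At baselines of about 86.7 µmol/L or above it would also leave the creatinine limb of the permission with nothing to cover, which makes it doubtful that it is what the text intends at every baseline.

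A second reply stands as a caution. A redacted block sits between the general renal stop and the transporter text in Section 2.3.1, and a figure at the end of Section 7.1.3 is not shown. Precedence could be stated there, so its absence from the full protocol cannot be asserted.

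A reader might also infer that the study-level rules contradict each other, with one participant halting the study under one rule and two needed under the other. The documents do not support that. The first trigger requires a 7.1.3 event considered related to the drug. The second has no relatedness condition, requires another abnormal marker, and can be reached by eGFR falls or by creatinine rises too small for the general rule. Either can operate, and neither says that a single related case is insufficient.

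**Conclusion.** The point holds at participant level. In the MAD part, a rise that meets Section 7.1.3 and is also a persistent rise of at least 30%, with other renal markers normal, falls under both a withdrawal instruction and a permission to continue. At the assumed baselines the overlap starts at a rise of 50% (50 µmol/L), 43% (60), 37% (70), 32.5% (80) and 30% (86.7 and above). The thresholds come from the protocol; the baselines are illustrative. Rises inside only one rule's range, and rises with another abnormal marker, are not in conflict.

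The study-level consequence is limited. A case considered related would stop dosing under Section 7.1.2 while Section 2.3.1 would let that participant go on. Whether this arises depends on a causality judgement, so nothing firmer can be said about whether the MAD part would complete.

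The conclusion is subject to the redacted text. It still needs correcting before MAD dosing, because it concerns an anticipated renal signal and a stopping decision that cannot be reversed.

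**What to change.** Reconcile the kidney entry in Section 2.3.1 with Sections 7.1.2 and 7.1.3 so that each creatinine result in the MAD part leads to one participant-level action. State the precedence between the general withdrawal rule and the transporter rule, and how a participant handled under the transporter rule relates to the one-participant stop in Section 7.1.2. Use identical wording in Section 2.3.1 and Section 7.1, including the individual rule for a change of 30% or more with another abnormal marker. If the redacted text already settles precedence, the sponsor should confirm this and repeat it in Section 7.1.3. Which rule governs is a decision for the sponsor's clinical team, and no view on it is offered here.

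The cost is amended wording in these sections. No new tests, visits or participants are needed.
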